### 9.2 Methods and Timing for Assessing, Recording, and Analyzing Safety Parameters

#### 9.2.1 Adverse Events

Any adverse events occurring as a result of obtaining blood samples will require clinical review, monitoring and treatment as needed until resolution or stabilization, and assessment for severity and relatedness. Subjects will be asked about final resolution of symptoms upon completion of each visit.

#### **Adverse Event:**

ICH E6 defines an AE as any untoward medical occurrence in a subject or clinical investigation participant administered a pharmaceutical product regardless of its causal relationship to the study treatment. An AE can therefore be any unfavorable and unintended sign (including an abnormal laboratory finding), symptom, or disease temporally associated with the use of medicinal product. The occurrence of an AE may come to the attention of study personnel during study visits and interviews of a study recipient presenting for medical care, or upon review by a study monitor.

All AEs including local and systemic reactions not meeting the criteria for "serious adverse events" will be captured on the appropriate CRF. Information to be collected includes event description, time of onset, clinician's assessment of severity, relationship to study product (assessed only by those with the training and authority to make a diagnosis, which would include MD, PA, Nurse Practitioner, DO, or DDS), and time of resolution/stabilization of the event. All AEs occurring while on study will be documented appropriately regardless of relationship. All AEs will be followed to stabilization or resolution.

Any medical condition that is present at the time that the subject is screened will be considered as baseline and not reported as an AE. However, if it deteriorates at any time during the study, it will be recorded as an AE.

All AEs will be graded for severity and relationship to study product.

FDA defines an AE as any untoward medical occurrence associated with the use of a drug in humans, whether or not considered drug related.

**Severity of Event:** All AEs will be assessed by the clinician using a protocol defined grading system. For events not included in the protocol defined grading system, than the following guidelines will be used to quantify intensity.

- Mild: events require minimal or no treatment and do not interfere with the subject's daily activities.
- Moderate: events result in a low level of inconvenience or concern with the therapeutic measures. Moderate events may cause some interference with functioning.
- Severe: events interrupt a subject's usual daily activity and may require systemic drug therapy or other treatment. Severe events are usually incapacitating.
- Life threatening: any adverse drug experience that places the subject or subject, in the view of the investigator, at immediate risk of death from the reaction as it occurred, i.e., it does not include a reaction that had it occurred in a more severe form, might have caused death.

Changes in the severity of an AE will be documented to allow an assessment of the duration of the event at each level of intensity to be performed. Adverse events characterized as intermittent will require documentation of onset and duration of each episode.

**Relationship to Study Products:** The clinician will assess an AE's relationship to influenza vaccine as part of the documentation process, but it is not a factor in determining what is or is not reported. All AEs will have their relationship to study product assessed using the terms: related or not related using the following guidelines:

- Related – There is a reasonable possibility that the study product caused the adverse event. Reasonable possibility means that there is evidence to suggest a causal relationship between the study product and the adverse event.
- Not Related – There is not a reasonable possibility that the study product caused the event.

Adverse events will be followed until resolved or considered stable. Any adverse event listed by the vaccine manufacturer as a contraindication to further doses of the vaccine will be considered an adverse event for the study. Any adverse event listed in the VAERS Table of Reportable Events Following Vaccination found using the following link [http://vaers.hhs.gov/resources/VAERS\\_Table\\_of\\_Reportable\\_Events\\_Following\\_Vaccination.pdf](http://vaers.hhs.gov/resources/VAERS_Table_of_Reportable_Events_Following_Vaccination.pdf) that occurs within the specified time period after vaccination or, if in the judgment of the PI, any unexpected reaction to the vaccine will be reported to VAERS with a copy faxed or emailed to the DMID CPM and MO at time of VAERS reporting. These reports will be made using the timelines outlined at [https://vaers.hhs.gov/resources/VAERS\\_Table\\_of\\_Reportable\\_Events\\_Following\\_Vaccination.pdf](https://vaers.hhs.gov/resources/VAERS_Table_of_Reportable_Events_Following_Vaccination.pdf).

All adverse events that meet the reporting requirements of the Institutional Review Board will be reported to the IRB within 10 days of the investigator learning of the event as delineated by the requirements listed on the Emory IRB website at: <http://www.irb.emory.edu/documents/AE-PD-UPchart.pdf>. These events will also be faxed or emailed to the Clinical Project Manager at time of IRB reporting. Per these guidelines, these adverse events would include those that are unanticipated, related to the study intervention and involve risk to the study participant

All Adverse events not meeting the reporting requirements of the Emory IRB will be reported to the clinical project manager periodically in monthly clinical reports and to the IRB periodically at annual continuing reviews.

#### 9.2.2 Serious Adverse Events

**Serious Adverse Event (SAE):** Serious Adverse Events will be collected from the time the participant begins the study until study completion, or until the participant withdraws from the study. SAE's will be documented on the Adverse Event form and reported to the DMID CPM and MO.

- All deaths and life-threatening events, regardless of relationship will be recorded on the SAE form and sent by fax to DMID CPM and MO within 24 hours of site awareness of the death or life-threatening event.
- All other SAEs, regardless of relationship will be recorded on the SAE form and sent by fax within 72 hours of becoming aware of the event.

A Serious Adverse Event is defined as an AE meeting one of the following conditions:

- Death during the period of protocol defined surveillance
- Life Threatening Event (defined as a subject at immediate risk of death at the time of the event)

- An event requiring inpatient hospitalization or prolongation of existing hospitalization during the period of protocol defined surveillance
- Results in congenital anomaly or birth defect
- Results in a persistent or significant disability/incapacity.
- Any other important medical event that may not result in death, be life threatening, or require hospitalization, may be considered a serious adverse experience when, based upon appropriate medical judgment, the event may jeopardize the subject and may require medical or surgical intervention to prevent one of the outcomes listed above. Examples of such medical events include allergic bronchospasm requiring intensive treatment in an emergency room or at home, blood dyscrasias or convulsions that do not result in inpatient hospitalization, or the development of drug dependency or drug abuse.

Events **not** considered to be serious adverse events are hospitalizations for the:

- routine treatment or monitoring of the studied indication not associated with any deterioration in condition.
- treatment, which was elective or pre-planned, for a pre-existing condition that is unrelated to the indication under study and did not worsen
- treatment on an emergency, outpatient basis for an event **not** fulfilling any of the definitions of serious given above and **not** resulting in hospital admission

All SAEs will be followed until satisfactory resolution or until the PI or co-investigator deems the event to be chronic or the subject to be stable. All SAEs will be reported to the Vaccine Adverse Event Reporting System (VAERS).

The DMID Medical Officer will review and assess the SAE for regulatory reporting and potential impact on the study subject safety and protocol conduct.

### **9.2.3 Other Adverse Events (If applicable)**

Not Applicable

### **9.3 Reporting Procedures and Safety Oversight**

This is a minimal risk study. Due to its nature very few, if any, serious adverse events are likely to be chronologically or causally related to study procedures, and any adverse events that do occur are likely to be mild, transient, and self-limiting. Therefore, adverse events, including serious adverse events, will be collected and reported to the IRB/IEC and DMID except for anticipated reactions noted in Section 9.2.1, an Independent Safety Monitor will not be required, and a formal Safety Monitoring Committee will not be constituted. All Adverse events will be communicated to the DMID and to the IRB as delineated by Emory Internal Review Board reporting requirements stated in section 9.2.1 and 9.2.2.

### **9.3.1 Reporting of Pregnancy**

A negative urine pregnancy testing is required for all women of childbearing potential prior to participating in the study. A urine pregnancy test will be performed at the screening visit and subsequently at any visit if the visit occurs +14 days after the last pregnancy test visit. If a subject becomes pregnant after enrollment in the study or reports it to the research team, the pregnancy will be reported as stated in section 9.3. Pregnant subjects will be withdrawn from the study and pregnancy will be followed for safety monitoring monthly to the point of pregnancy outcome.

## **9.4 Type and Duration of Follow-up of Participants after Adverse Events**

Clinical studies at Emory University are compliant with ICH E6 guidelines for Good Clinical Practice.

Adverse events will be documented and reported according to the DMID and Emory IRB policies (as described in section 9.2.1 and 9.3). All AEs and SAEs will be followed until resolved, return to baseline or stable as determined by the study team. The occurrence of AEs and the status of existing AEs will be assessed at each study visit and events are recorded in the regulatory binder. Subjects will be encouraged to contact study staff of any health changes that may occur between study visits. An unscheduled visit or telephone follow-up may occur depending on the adverse event.

## **9.5 Halting Rules**

This is a minimal risk study. It is not anticipated that there will be a need to halt the study due to SAEs. The study will be halted if the following occurs:

- One or more participants have laryngospasm, bronchospasm, or anaphylaxis associated with study procedure and occurring within 72 hours post study procedure;
- Any SAE associated with study product or procedure;
- Two or more participants experience the same or similar severe or life-threatening AE judged to be associated with study procedure.

## **9.6 Safety Oversight**

Serious and severe adverse events will be reported to DMID. DMID has the authority to stop study enrollment, vaccinations and procedures if AEs are reported that meet halting criteria.

## **9.7 Independent Safety Monitor (ISM)**

Not Applicable.

## 10 CLINICAL MONITORING

Purpose: to protect the rights and well-being of human subjects in this study; to ensure that data are accurate, complete and verifiable from source documents; to ensure that conduct is in compliance with the currently approved protocol/amendments, with Good Clinical Practice, and with regulatory requirements.

### 10.1 Site Monitoring Plan

Site monitoring will be conducted using the DMID tools provided to ensure that human subject protection, study procedures, laboratory procedures, and data collection processes are of high quality and meet sponsor, GCP/ICH, and regulatory guidelines, and that the study is conducted in accordance with the protocol and sponsor standard operating procedures. DMID, the sponsoring agency, or its designee will conduct site-monitoring visits as defined in the CQMP.

A protocol-specific Clinical Quality Management Plan (CQMP) has been approved for this study by DMID which provides details for site monitoring. The Quality Assurance (QA) plan will be implemented by a weekly review of source documents by the CRC to determine adherence to protocol requirements. The Quality Control (QC) plan will be implemented by daily observation and documentation of the site's work processes by study staff, to ensure that accepted procedures are followed.

Site visits may be made at standard intervals as defined by DMID and may be made more frequently as directed by DMID. Monitoring visits will include, but are not limited to, review of regulatory files, sample tracking log, CRFs, informed consent forms, medical and laboratory reports, and protocol compliance. Study monitors will meet with investigators to discuss any problems and actions to be taken and document visit findings and discussions. Emory University IRB and other regulatory agencies may conduct study monitoring visits.

## 11 STATISTICAL CONSIDERATIONS

For this study we will assess immunologic responses in the periphery (blood). These responses contain a variety of immunologic assays with different types of response output. Hence our primary data analytic strategy will be the use of longitudinal data analysis methods to determine the temporal course of a given response measurement and factors associated with heterogeneity in that temporal course. Study outcomes will be measured using numerical data from laboratory assays including flow cytometry and ELISPOT assays. A detailed data management system will utilize general linear mixed models for continuous responses to assess differences among time points.

### 11.1 Study Hypothesis

To investigate the longevity of humoral immunity to influenza virus in humans. Our overarching hypothesis is that an understanding of how long-term humoral immunity to influenza virus is generated and maintained is essential for the development of a “universal” vaccine against influenza virus. This aim will be accomplished by measuring the total influenza-specific, memory B-cells and serum antibody levels over extended periods following vaccination.

### 11.2 Sample Size Considerations

In our preliminary studies, we found that vaccine-elicited plasmablasts that are specific to the stalk region of HA (the broadly protective region) were induced in 20% of subjects after receiving the annual inactivated trivalent influenza vaccine. This analysis was done on only 20 subjects and we would like to test the consistency of our observation with a larger sample size of 50.

### 11.3 Planned Interim Analysis

Not Applicable

### 11.4 Final Analysis Plan

We will be utilizing the paired Student's *t*-test to determine whether the observed increase in serum antibody titers from baseline to 4 weeks after vaccination is significant or not. We do not anticipate any major change in our analysis strategy. For all of this analysis we will work the Emory/UGA CEIRS Data Management Team headed by [name] using the approved Data Management Plan for this contract.

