#### 3.2 Outcome Measures

##### 3.2.1 Primary Outcome Measures

- Determine the percentage of subjects achieving seroconversion, defined as the percentage of subjects with either a pre-vaccination HI titer < 1:10 and a post-vaccination HI titer > 1:40 or a pre-vaccination HI titer > 1:10 and a minimum four-fold rise in post-vaccination HI antibody titer (day 0, 28).

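### Section 11 plans no estimate or interval for the primary outcome, the seroconversion percentage, and the one test in 11.4 says little about it

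*Combined protocol and SAP*

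**What the plan says.** Section 3.2.1 lists one primary outcome measure: "Determine the percentage of subjects achieving seroconversion". Each participant is a yes or a no. A participant with a low pre-vaccination HI titer must pass a fixed post-vaccination level. A participant with a higher starting titer needs at least a four-fold rise. The days given are 0 and 28.

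Section 11.4, the Final Analysis Plan, names one analysis: a paired Student t-test to "determine whether the observed increase in serum antibody titers from baseline to 4 weeks after vaccination is significant or not". It expects no major change of strategy. It does not say which assay or strain is tested, or whether titers are log-transformed.

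The introduction to Section 11 describes longitudinal methods and "general linear mixed models for continuous responses to assess differences among time points". Section 11.1 concerns longevity. Section 11.2 starts from stalk-specific plasmablasts, "induced in 20% of subjects after receiving the annual inactivated trivalent influenza vaccine", and wants to "test the consistency of our observation with a larger sample size of 50". Seroconversion appears nowhere in Section 11.

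**The concern.** The primary outcome is a proportion. The stated final analysis covers the same interval, baseline to four weeks, but tests whether a mean change differs from zero. A reader who follows Section 11 obtains a p-value for titers and no inference on the outcome that the protocol calls primary.

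This goes beyond missing detail, because the test that is written down cannot answer the primary question. At the planned size it will be significant for almost any real response to the vaccine, whether few or most participants seroconvert. If that p-value became the headline, the precision of the seroconversion estimate would go unreported.

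**Working it through.** **Inputs.** From the documents: the seroconversion definition (3.2.1), the paired t-test (11.4), n = 50 (11.2) and the enrollment ceiling of 70 (Section 5). Assumed, because the documents do not state them: two-sided 5% level, log2 titers, and, in steps 3 and 4 only, an SD of the log2 rise between 1.0 and 2.0.

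**1. The plan's own figures.** The ceiling reproduces: 3 × 10 + 2 × 20 = 70. The 50 cannot be reproduced, since no significance level, power, alternative or precision target is given. It concerns the plasmablast rate in any case. The documents therefore give no size or precision calculation for seroconversion.

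**2. A check that needs no SD assumption.** Let k of n participants rise exactly two-fold (1 log2 unit) and the others not change. With f = k/n, the mean rise is f, the SD is √[f(1 − f) × n/(n − 1)], and so t = √[(n − 1) × f/(1 − f)].

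- k = 25, n = 50: t = √(49 × 0.5/0.5) = 7.0 on 49 df, p ≈ 7e-9.
- k = 4, n = 50: t = √(49 × 0.08/0.92) = 2.06, p = 0.044.
- k = 4, n = 70: p = 0.045.

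Seroconversion is 0% in all three. A two-fold rise is short of four-fold, and doubling a titer below 1:10 leaves it below 1:20, short of the 1:40 level.

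**3. Smallest significant mean rise.** This is t(0.975, n − 1) × SD/√n. At n = 50 it is 0.284 × SD. For SDs of 1.0, 1.5 and 2.0 log2, that is a geometric mean rise of 1.22-, 1.34- or 1.48-fold.

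**4. Power against the share with a four-fold rise (illustration only).** Rises are drawn as normal and rounded to whole two-fold steps, n = 50, 20,000 simulated trials per row. The share with at least a four-fold rise is 1 − Φ((1.5 − mean)/SD).

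| SD (log2) | Mean log2 rise | Share with ≥4-fold rise | Power of t-test |
|---|---|---|---|
| 1.0 | 0.4 | 14% | 76% |
| 1.5 | 0.6 | 27% | 78% |
| 1.5 | 1.0 | 37% | 99.5% |
| 1.5 | 1.5 | 50% | 100% |
| 1.5 | 2.0 | 63% | 100% |
| 2.0 | 0.8 | 36% | 78% |

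The shares depend on the rounding. At mean 1.0 and SD 1.5 without rounding, the share is 1 − Φ((2 − 1)/1.5) = 25%, with power 99.6%.

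**5. What an interval would show.** Exact (Clopper-Pearson) 95% intervals, assuming independent participants and no missing titers:

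| Seroconverted | Percentage | 95% CI |
|---|---|---|
| 10/50 | 20% | 10.0 to 33.7% |
| 25/50 | 50% | 35.5 to 64.5% |
| 40/50 | 80% | 66.3 to 90.0% |
| 35/70 | 50% | 37.8 to 62.2% |

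The largest half-width is about 14.5 points at n = 50 and 12.2 points at n = 70. At n = 50 the intervals for 20%, 50% and 80% do not overlap.

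**The case against.** Several points on the other side stand.

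- A reader might infer that the study will never report a seroconversion percentage. The documents do not support that: 3.2.1 commits to determining it, and Section 15.4 promises a comprehensive analysis. What Section 11 lacks is the estimate's interval, denominator and strain rule, and its place in the conclusion.
- A reader might also infer that the t-test is the designated primary analysis. No section says so. Section 11 calls longitudinal methods its primary strategy, and 11.4 speaks of serum antibody titers without naming HI. The test could serve the endpoint IgG titers at Days 0 and 28 in 3.2.2, where it would be a reasonable choice. That still leaves the primary outcome with no planned analysis.
- This is a single-arm, observational study of licensed vaccine with no seroconversion threshold or decision rule, so no result is labeled good or poor. That limits the consequences. It also makes an estimate with an interval more useful than a test against no change.
- The shares in step 4 are not seroconversion rates. They rest on assumed SDs and cover only the four-fold part of the definition; the low-baseline part needs a baseline distribution that the documents do not give. Step 2 needs no SD, but it does use the log2 scale.

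**Conclusion.** The concern holds in this form: the only primary outcome has no planned inference in Section 11, and the one final analysis named there, over the same interval, addresses a different quantity. A significant result is compatible with 0% seroconversion (p ≈ 7e-9 with 25 of 50 rising two-fold), given log2 titers and a two-sided 5% level. The power figures illustrate how little the test discriminates and depend on the assumed SD: with SD 1.5, about 78% power when 27% have at least a four-fold rise and over 99% when 37% do. The finding does not extend to saying that the percentage will go unreported or that the protocol names the t-test as its primary analysis. The HI data needed are already to be collected, so the gap is in the plan and can be closed.

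**What to change.** In 11.4, make the primary analysis the Day 28 seroconversion percentage for each vaccine strain, among participants with both Day 0 and Day 28 HI results. Show numerator, denominator and a 95% CI; an exact interval is one suitable choice. Base the primary conclusion on the percentage and its interval, and keep the paired titer comparison as supportive, naming its assay and scale.

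Two details need a sentence each:

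- **Repeat enrollment.** Section 5 lets people re-enroll under new identifiers and counts them again, so records are not independent. Either use each person's first enrollment only, or use an interval that allows for clustering by person.
- **Strains across seasons.** Section 2.1 notes that the vaccine is updated each season. State whether results are pooled across seasons, for example by subtype. The 12-to-15-point half-widths apply only to pooled totals of 50 to 70. A strain used in a single season would have 10 or at most 20 participants, where 5/10 gives 18.7 to 81.3% and 10/20 gives 27.2 to 72.8%.

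No new visits, samples or assays are needed, since Section 8.2 already has HAI titers measured at every time point. The downside is presentational: the headline becomes an interval of up to about 12 to 15 points either side, wider if only first enrollments count, in place of a near-certain p < 0.05.

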##### 3.2.2 Secondary Outcome Measures

Investigation of the longevity of humoral immunity to influenza virus in humans will be performed by:

- Measuring influenza hemagglutinin stem-specific and head-specific memory B-cells and serum antibody levels at days 0, 28, and 180.
- For serum antibody responses directed against the HA head or stem regions, we will determine the endpoint IgG titers at days 0, 28 and 180 after vaccination.  
For memory B cells, we will determine the frequency of HA head- or stem-specific IgG-secreting memory B cells per total IgG-secreting cells at days 0, 28 and 180 after vaccination.
- Plasmablast responses against either the HA head or stem antigens will be determined by direct ex vivo ELISPOT at day 7 after vaccination.
- Expression of human influenza-specific monoclonal antibodies from Day 7 plasmablasts and assessing their functional by ELISA, HAI, and virus neutralization assays.

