### 7.3 Follow-up and Final Visits

#### Follow-up visits: Days 7, 14, 28, 90, 180.

- Study participants will be asked to return for five follow up visits, with the respective window periods, per the table below:

Day	7	14	28	90	180
Time point					
Window	+/- 1	+/- 2	+/- 3	+/- 10	+/- 14 (a 90 day window expansion is being requested)
Blood Volume	96mL	96mL	64mL	64mL	64mL

- Medical history will be reviewed and updated as appropriate.
- All concomitant medications taken since the previous study visit will be recorded on the appropriate data collection form. Previously recorded medications will be updated as appropriate.
- Study personnel will discuss with participants and assess and record all AE/SAEs. Previously recorded AE/SAEs will be updated as appropriate.
- Approximately the amount of venous blood, as indicated by the table above, will be collected for research assays.
- Targeted physical exam will be done only as dictated by a change in medical history.
- A urine pregnancy test will be performed on all female participants of childbearing potential

for any visit longer than 14 days from the last pregnancy test..

- Follow-up visits were also halted, which impacted several participants' Day 180 follow-up visit.
- We are requesting that the windows for the Day 180 visit be extended by 90 days.
- Extending the window for the Day 180 follow-up visits would allow samples from participants whose visits were halted at this time point to be collected once the Emory restrictions regarding COVID-19 are lifted and staff can reasonably collect samples, dependent upon when the University and applicable Unit and School allow. The scientists feel that the samples, even if a few months late, will greatly help evaluate the longevity of the responses to flu vaccines.
- Study activities will not be changed, just the timing of the Day 180 visit.

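### The only test named in the Final Analysis Plan stops at 4 weeks, and no Day 180 contrast is tied to the mixed model that could answer the longevity question

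*Combined protocol and SAP*

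**What the plan says.** Section 3.1 lists longevity as the secondary objective. Section 11.1, headed as the study hypothesis, opens with "To investigate the longevity of humoral immunity to influenza virus in humans" and says the aim will be met by "measuring the total influenza-specific, memory B-cells and serum antibody levels over extended periods following vaccination". Section 3.2.2 gives the schedule: "Measuring influenza hemagglutinin stem-specific and head-specific memory B-cells and serum antibody levels at days 0, 28, and 180".

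The analysis text is in two places. Section 11 names as its primary strategy "longitudinal data analysis methods to determine the temporal course of a given response measurement and factors associated with heterogeneity in that temporal course", and adds "general linear mixed models for continuous responses to assess differences among time points". It gives no outcome, scale, contrast, covariance structure or significance level for that model. Section 11.4 then names one test, a paired t-test of "whether the observed increase in serum antibody titers from baseline to 4 weeks after vaccination is significant or not", and expects no major change of strategy.

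Three other passages bear on the analysis. Section 7.3 allows 14 days either side of Day 180 and requests a further 90 days for visits halted by the pandemic, on the ground that late samples still inform longevity. Section 5 lets people who complete the study re-enroll under a new identifier and count again. Section 3.2.1 sets the primary outcome as HI seroconversion between Days 0 and 28.

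**The concern.** A test that compares Day 0 with Day 28 returns the same result whatever happens afterwards, so the named test cannot bear on longevity. The model that does reach Day 180 is described in general terms, and nothing says which of its outputs is the durability result. If the analyst reports one overall test of time, the early rise can make it significant by itself. If the analyst reports comparisons, the plan does not say which visits, which of the head and stem IgG titers and memory B-cell frequencies, or which measure of persistence counts. The choice would then be made with the data in view.

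The hypothesis sentence in 11.1 does not help. It asserts that understanding long-term immunity is essential for a universal vaccine, and no result of this study could confirm or refute that. The documents also do not say how a sample drawn well after Day 180 enters the analysis, although the extension was requested for the longevity question.

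**Working it through.** **Reproducing the plan's figures.** Section 11.2 says "we would like to test the consistency of our observation with a larger sample size of 50", with no alpha, power, effect size or precision target, so 50 cannot be derived. The enrollment total does reproduce: 3 × 10 + 2 × 20 = 70. I use n = 50 and n = 70.

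**Assumptions (none is in the documents).** Log2 titers; Day 28 rise of 1 or 2 log2; within-subject SD 1.0 or 1.5; between-subject SD 1.5; independent subjects; no dropout; two-sided 0.05; 1,500 simulated trials per setting. Persistence means Day 0/28/180 values of 0, rise, rise. Loss means 0, rise, 0.

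**1. Paired t-test, Day 28 minus Day 0.** With rise 1, SD 1.5 and n = 50, the SD of the difference is 1.5 × √2 = 2.12, the SE is 2.12/√50 = 0.300, and the noncentrality is 1/0.300 = 3.33, giving power of about 0.90. Day 180 does not appear in the formula.

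**2. Overall time test, three visits.** The noncentrality is n × Σ(mean − grand mean)² / SD².
- Persistence (0, 1, 1): the sum of squares is 2/3.
- Loss (0, 1, 0): the sum of squares is 2/3.
- In both cases, 50 × (2/3) / 2.25 = 14.8 on 2 and 98 degrees of freedom, so power is about 0.93.

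On this schedule the overall test has identical power under the two opposite outcomes.

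**3. Simulated rejection rates, n = 50, rise 1, SD 1.5, three visits.**

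| Analysis | Full persistence | Half lost | Complete loss |
|---|---|---|---|
| t-test, Day 28 vs 0 | 0.90 | 0.91 | 0.90 |
| Overall time test | 0.93 | 0.86 | 0.93 |
| Day 180 vs 0 | 0.91 | 0.38 | 0.04 |
| Day 180 vs 28 | 0.06 | 0.39 | 0.93 |

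The average estimated Day 180 minus Day 0 change was 1.00 log2 under persistence and −0.01 under loss. With all six visits the overall test rejects in 0.94 and 0.97. With rise 2 the t-test and overall test reject in 1.00 under both outcomes, and Day 180 vs 0 rejects in 1.00 against 0.05 to 0.06 (n = 50). The pattern was the same in every setting, including n = 70.

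**4. Precision of the waning ratio (Day 180/Day 28).**
- Assumed SD 1.8 and correlation 0.85: SD of the difference = 1.8 × √(2 × 0.15) = 0.986. The half-width is 2.01 × 0.986/√50 = 0.280 log2, a factor of 2^0.280 = 1.21. At n = 70 the factor is 1.18.
- Within-subject SD 1.0 to 1.5, as in step 3: SE = SD × √(2/50) = 0.200 to 0.300. With a t multiplier of 1.98 the half-width is 0.397 to 0.595 log2, a factor of 1.32 to 1.51. At n = 70 it is 1.26 to 1.42.

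**5. Missing Day 28 samples.** If 10% of 50 lack Day 28 (assumed), the paired test uses 45: with SD of the difference 1.8, the SE is 1.8/√45 = 0.268. A generalised least squares fit using the other visits gave 0.257. The variance ratio is (0.257/0.268)² = 0.92, about 8% lower, which is a minor gain.

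**The case against.** A reader might infer that everything planned would look the same whether immunity lasts or disappears. The documents do not support that. Section 11 sets out to determine the temporal course of each response, and durable and lost immunity are different courses. Estimates by visit and pairwise differences from that model separate the two sharply, as the last two rows of the table show. The sameness holds only for the t-test and for a mixed model reduced to one overall test, which the text does not require. Nor does section 11.4 say that it replaces section 11.

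Longevity is also the secondary objective. The t-test covers the window of the primary seroconversion outcome, so a 4-week test is not misplaced in itself. Section 3.2.3 lists exploratory work on clones that persist to late visits, so persistence is on the sponsors' minds. In a single-arm observational study, estimates matter more than rejection rates.

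All of that stands, and it narrows the point to prespecification. It does not remove it: no section names a Day 180 contrast, a retention or decay measure, a definition of persistence, or a rule for several comparisons. The exploratory items name no test.

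**Conclusion.** The concern holds in this limited form. The one named test cannot inform longevity. The section 11 model can, but nothing says which of its outputs answers the question, and an overall time test would not. This is a gap in the analysis of the secondary objective and the stated hypothesis; the planned samples themselves can address it.

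That the t-test ignores Day 180 is true by construction, and the equal power of the overall test under full persistence and complete loss follows from the three-visit design. The rejection rates and precision figures depend on the assumed rise, SDs and correlations. At the noisier setting with n = 50, losing half of a 1 log2 rise is detected by either Day 180 contrast less than 40% of the time, which is a further reason to report intervals. All figures assume independent subjects. Re-enrollment breaks that assumption to an extent the documents do not give.

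**What to change.** In section 11.4, make the section 11 mixed model the final analysis, applied to log titers and memory B-cell frequencies and using all available visits. For head- and stem-specific responses, report three contrasts with 95% confidence intervals:
- Day 28 minus Day 0 (rise);
- Day 180 minus Day 28 (waning);
- Day 180 minus Day 0 (durable gain).

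Name the two Day 180 contrasts as the longevity analysis and one contrast on one outcome as leading. Three contrasts on four outcomes make 12 comparisons before strains are counted, so present the rest as estimates.

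Visit as a plain factor would pool on-time Day 180 samples with those from the expanded window and blur the waning contrast. Model the actual sampling day, or repeat the analysis without the late samples. Link identifiers across seasons and use a person-level random effect for people who re-enroll. Reword 11.1 as a hypothesis about the Day 180 contrasts. Keep the paired t-test as a check on the 4-week rise.

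The cost is wording in 11.1 and 11.4 and a few model statements, with no new samples, visits or participants. The drawback is a longer list of contrasts, which naming a leading one keeps in hand.
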